6.1.3.2.2. Laboratory Evaluation of Liver Disease

Laboratory data will be analyzed and summarized by treatment group using both quantitative and qualitative methods. Summaries of laboratory data will be provided for the FAS and will include all available data. The analysis will be based on values reported in conventional units. When values are below the LOQ, they will be listed as such, and the closest imputed value will be used for the purpose of calculating summary statistics as stated in Section 3.7. Hemolyzed test results will not be included in the analysis, but they will be listed in by-participant laboratory listings.

By-participant, by-visit listings for hematology, coagulation, and serum chemistry laboratory test results will be provided by participant ID number in chronological order. Values falling outside of the relevant reference range and/or having a severity grade of 1 or higher on the Gilead Grading Scale for Severity of Adverse Events and Laboratory Abnormalities will be flagged in the data listings, as appropriate.

Hematology: Platelets

Chemistry: Alanine aminotransferase (ALT/SGPT), aspartate aminotransferase (AST/SGOT), albumin, total bilirubin, direct bilirubin, creatinine

Coagulation Test: international normalized ratio (INR), prothrombin time (PT)

A separate by-participant, by-visit listing will be provided for additional laboratory tests including:

- Alpha-fetoprotein (AFP) level
- FibroTest®: alpha-2-macroglobulin, alpha-2-globulin (haptoglobin), apolipoprotein A1, gamma-glutamyl transpeptidase (GGT), and total bilirubin
- Enhanced Liver Fibrosis (ELF) panel: hyaluronic acid, amino-terminal propeptide of type III collagen, and TIMP-1

- Fasting lipid panel: low-density lipoprotein (LDL), high-density lipoprotein (HDL), triglycerides, total cholesterol
- Hemoglobin A1C (HbA1c)
- HOMA-IR (Fasting insulin x Fasting glucose / 405)
- LOXL2 levels

A shift table for Fibrotest stage (No or minimal fibrosis/Moderate fibrosis/Severe fibrosis) from baseline to postbaseline visits will be provided by treatment group.

A shift table for ELF class from baseline to postbaseline visits will be provided by treatment group. ELF classes are defined as:

- * Class F0-F2: score < 9.8;
- * Class F3: score in 9.8 - 11.3;
- * Class F4: score > 11.3.

FIB-4 index is calculated by:

$$\text{FIB-4 Index} = \text{round}((\text{age} \times \text{AST}) / (\text{platelet} \times \text{sqrt}(\text{ALT})), 0.01);$$

Where ALT is in unit of (U/L), platelet is in unit of ($\times 10^3/\text{uL}$), AST is in unit of (U/L), and age in years.

A shift table for FIB-4 class (defined as subjects with index score of $\geq 25\%$ increase, $\geq 25\%$ reduction at postbaseline from baseline, or the rest as no change from baseline; and baseline classes [< 1.3 , ≥ 1.3 and < 2 , ≥ 2 and ≤ 2.67 , > 2.67]) from baseline to postbaseline visits will be provided by treatment group.

AST to Platelet Ratio Index (APRI) will be calculated as:

$$\text{APRI} = \text{round}(\text{AST}/\text{AST ULN} \times 100 / \text{platelet}, 0.1);$$

Where ALT is in unit of (U/L), platelet is in unit of ($\times 10^3/\text{uL}$), AST ULN is AST upper limit of Normal with unit of (U/L).

For FIB-4 index and APRI calculation, the laboratory parameters need to be measured from the same blood draw. Age (years) should be the actual age at the date when laboratory values are taken.

6.1.3.2.2.1. Quantitative Summaries of Laboratory Results

Descriptive summary statistics (n, mean, SD, median, Q1, Q3, minimum, and maximum) will be provided by treatment group. For each laboratory test as specified in the study protocol, the mean, median, Q1, Q3, minimum, and maximum values will be displayed to the reported number of digits; SD values will be displayed to the reported number of digits plus 1.

In details, descriptive statistics will be provided for each laboratory test: Baseline values, values at each postbaseline visit, and change from baseline at each postbaseline visit.

Analysis visit windows are as defined in Section 3.8.2. In the case of multiple values in an analysis window, data will be selected for analysis as described in Section 3.8.3.

6.1.3.2.2.2. Graded Laboratory Values

The Gilead Grading Scale for Severity of Adverse Events and Laboratory Abnormalities (Version dated 01 April 2015) will be used for assigning toxicity grades (0 to 4) to laboratory results for analysis. Grade 0 includes all values that do not meet the criteria for an abnormality of at least Grade 1. Some laboratory tests have criteria for both increased and decreased levels and analyses for each direction (i.e., increased, decreased) will be presented separately.

Laboratory abnormalities are defined as values that increase at least 1 toxicity grade from baseline for any postbaseline value. If the relevant baseline laboratory value is missing, then any abnormality of at least Grade 1 will be considered a laboratory abnormality.

Laboratory data that are categorical will be summarized using the number and percentage of participants in the registry with the given response at baseline and each scheduled postbaseline visit. All graded laboratory abnormalities/Grade 3 or above abnormalities will be separately summarized (number and percentage of participants) by lab test and overall. Participants will be categorized according to the most severe postbaseline abnormality grade for a given analyte. The denominator for graded laboratory abnormality summaries is the number of participants with non-missing postbaseline values.

By-participant, by-visit listings for laboratory abnormalities will be provided by participant ID number in chronological order with all applicable severity grades displayed, and a separate listing for participants with severe (Grade 3 or Grade 4) laboratory abnormalities.

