#### **3.2. Discontinuation Criteria**

Registry participation will be discontinued in the following instances:

- Subjects who experience virologic relapse or re-infection defined as HCV RNA > LLOQ on two samples collected at least one week apart;
- Subjects who have a liver transplant;
- Subjects who request to discontinue for any reason; it is important to clearly determine and document the specific reason for withdrawal of consent;
- Discontinuation of the Registry and/or subjects at the request of Gilead, regulatory agency or an Institutional Review Board (IRB)/Independent Ethics Committee (IEC).

If a subject meets withdrawal criteria or discontinues participation for any reason, the subject should complete an Early Termination visit.

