## 4. SUBJECT POPULATION

### 4.1. Inclusion Criteria

Subjects must meet all of the following inclusion criteria to be eligible for participation in this study.

- 1) Willing and able to provide written informed consent;
- 2) Have either previously participated in a Gilead-sponsored HCV study and received a sofosbuvir-containing regimen without interferon; OR

At pre-selected sites only, have received an all-oral SOF-based regimen outside a clinical study. These subjects must have documentation of the regimen, start and end of treatment dates (month and year), and of having achieved SVR12

- 3) Have achieved SVR either in a Gilead-sponsored study, as defined in the treatment protocol; OR for subjects who enroll after receiving an all-oral SOF-based regimen outside a clinical study, SVR will be defined as HCV RNA < LLOQ approximately 12 weeks following last dose of treatment.
- 4) Have liver cirrhosis, as defined in the treatment protocol, and have not had a liver transplant after receiving a SOF-containing regimen; OR

Subjects who enroll after receiving an all-oral SOF-based regimen outside a clinical study, will have had cirrhosis as diagnosed prior to initiation of HCV treatment.

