### 6.2.4. Early Termination (ET) Visit

Subjects discontinuing the Registry for any reason should undergo the Early Termination (ET) visit. Subjects will be asked to come in fasting for this visit and the following procedures will be performed and documented:

- Complete Health Related Quality of Life (HRQoL) Surveys
- Conduct limited physical exam
- Collect information for liver disease assessment
- Obtain blood samples.
- Perform transient elastography (at sites with a Fibroscan®)
- Record any serious adverse events or adverse events that are related to protocol-required procedures

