**Appendix 2. Study Procedures Table**

Clinical Assessments	Day 1	Study Week										
		24	48	72	96	120	144	168	192	216	240	ET
Informed Consent a	X											
Quality of Life Surveys	X	X	X	X	X	X	X	X	X	X	X	X
Adverse Events Related to Procedures	X	X	X	X	X	X	X	X	X	X	X	X
Limited Physical Exam b	X	X	X	X	X	X	X	X	X	X	X	X
Liver Disease Assessment c	X	X	X	X	X	X	X	X	X	X	X	X
Endoscopy	X									X		
Transient Elastography d	X		X		X		X		X		X	X
Liver Biopsy e											X	
Laboratory Assessments												
HCV RNA	X	X	X	X	X	X	X	X	X	X	X	X
Viral Sequencing f	X	X	X	X	X	X	X	X	X	X	X	X
Chemistry g	X	X	X	X	X	X	X	X	X	X	X	X
Hematology (Platelets)	X	X	X	X	X	X	X	X	X	X	X	X
Coagulation Test (PT/INR)	X	X	X	X	X	X	X	X	X	X	X	X
Additional Tests h	X	X	X	X	X	X	X	X	X	X	X	X
HCV RNA Confirmation i							X					

- a Informed consent may be obtained prior to Day 1
- b Assessment of ascites, encephalopathy, height (at Day 1) and weight; calculated scores include BMI, CTP and MELD
- c Liver Disease Assessment: refer to protocol Section 6.3.5
- d At sites with a Fibroscan® equipment
- e **CCI**
- f Plasma will be collected for possible viral sequencing or other virology studies if indicated.
- g Includes ALT/SGPT, AST/SGOT, Albumin, Total bilirubin, Direct Bilirubin, Creatinine
- h Includes  $\alpha$ -fetoprotein level, FibroTest®, ELF panel, lipid panel, hemoglobin A1C, HOMA-IR and LOXL2
- i Only in subjects with HCV RNA >LLOQ
- j For subjects who consent

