6.1.3.2.3. Child-Turcotte-Pugh (CTP) Score and MELD Score

Laboratory assessment data will be used to determine the CTP score and MELD score. CTP will be calculated as a summation of all points assigned as shown in Table 6-1.

Table 6-1. Child-Turcotte-Pugh Score Calculations

Parameter	Points Assigned		
	1	2	3
Ascites	Absent	Slight	Moderate

Total Bilirubin	< 2 mg/dL (< 34.2 micromol/liter)	2 - 3 mg/dL (34.2 - 51.3 micromol/liter)	> 3 mg/dL (> 51.3 micromol/liter)
Albumin	> 3.5 g/dL (> 35 g/liter)	2.8 - 3.5 g/dL (28 - 35 g/liter)	< 2.8 g/dL (< 28 g/liter)
Prothrombin Time (Seconds over control, PT) OR International normalized ratio (INR)*	< 4 < 1.7	4 – 6 1.7 – 2.3	> 6 > 2.3
Encephalopathy	None	Grade 1 - 2	Grade 3 - 4

* INR is chosen for this study’s CTP calculation per eCRF.

A total CTP score of 5-6 is considered grade A (compensated), 7-9 is grade B (significant functional compromise/decompensated), and 10-15 is grade C (decompensated). A missing CTP score/cirrhosis status not available will be displayed as “Unknown” grade category in summaries. The proportion of participants in each CTP score category (A [5-6], B [7-9] and C [10-15]) will be summarized by visit for each treatment group. A shift table of CTP category by treatment group will be provided as well. By-participant, by-visit listing of CTP score results will be provided by participant ID number in chronological order.

MELD score will be calculated at each visit. Table with descriptive statistics (n, mean, SD, median, Q1, Q3, minimum, and maximum) for MELD score and change from baseline by visit for each treatment group will be provided. A shift table for MELD score category (\geq or <15) at each postbaseline visit from baseline will also be provided by treatment group. MELD score results will be listed by participant ID number and visit.

The MELD score will be calculated using the following formula:

$$10 \times \{[0.957 \times \text{Ln}(\text{Scr})] + [0.378 \times \text{Ln}(\text{Tbil})] + [1.12 \times \text{Ln}(\text{INR})] + 0.643\},$$

Where Scr = serum creatinine (in mg/dL), Tbil = Total Bilirubin (in mg/dL), INR = international normalized ratio, and Ln = natural log. If any lab value was less than 1.0, then it will be set to 1.0 in the calculation. If the participant received dialysis at least twice in the past week, then Scr will be set to 4.0 mg/dL in the above formula. The result will be rounded to the nearest whole number.

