6.4.3. Transient Elastography

A transient elastography will be performed to assess the liver elasticity at Day 1 (+ 4 weeks) and every 48 weeks (+/- 4 weeks) through Week 240 at sites with a Fibroscan® or comparable equipment. Descriptive statistics (n, mean, SD, median, Q1, Q3, minimum, and maximum) will be provided by visit and by treatment group as follows:

- Baseline values
- Values at each postbaseline visit
- Change from baseline at each postbaseline visit

Analysis visit windows as defined in Section 3.8.2. Data record with a procedure date prior to the most recent HCV treatment end date will be excluded in the above summary table. In the case of multiple values in an analysis window, data will be selected for analysis as described in Section 3.8.3.

The results of the transient elastography including the reported interquartile range will be listed by participant ID number and visit. Data record with a procedure date prior to the most recent HCV treatment end date will be flagged.

The shift table for fibroscan category by treatment group will be provided based on following:

- Category F0 to F2: 9.5 kPa or less
- Category F3: 9.6 to 12.5 kPa
- Category F4: greater than 12.5 kPa

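### Results measured after an on-study liver transplant are not excluded from the SAP's laboratory, CTP, MELD, fibrosis-marker and elastography summaries

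*SAP*

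**What the plan says.** Protocol 3.2 lists "Subjects who have a liver transplant" among the reasons for ending participation, and continues: "If a subject meets withdrawal criteria or discontinues participation for any reason, the subject should complete an Early Termination visit". Protocol 6.2.4 has the same scope: "Subjects discontinuing the Registry for any reason should undergo the Early Termination (ET) visit". The ET list there contains the limited physical exam, blood samples and, at sites with the device, transient elastography. The procedures table (protocol Appendix 2) marks chemistry, platelets, PT/INR and the additional tests, including FibroTest and ELF, at ET. Its footnote to the physical exam says "calculated scores include BMI, CTP and MELD".

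SAP 3.8.2 assigns observations to windows by study day. SAP 3.8.3 takes the record closest to the nominal day when one value is needed. On laboratory data, SAP 6.1.3.2.2 says: "Summaries of laboratory data will be provided for the FAS and will include all available data". The only records it drops are hemolyzed samples. FIB-4 and APRI are defined in the same section.

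SAP 6.1.3.2.3 adds by-visit CTP and MELD summaries, a MELD shift table cut at 15, and this: "A shift table of CTP category by treatment group will be provided as well". It has no record exclusion. SAP 6.4.3 has one, for elastography only: "Data record with a procedure date prior to the most recent HCV treatment end date will be excluded in the above summary table".

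Transplant is named in SAP 6.1.3.2.1 as a progression event and has its own Kaplan-Meier table.

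**The concern.** Progression or regression of liver disease, judged by clinical and laboratory parameters, is a primary endpoint (SAP 6.1.1). The Kaplan-Meier analyses in SAP 6.1.3.2.1 deal with adverse liver events, so regression can be seen only in the change-from-baseline and shift tables for laboratory markers, scores and stiffness. Those tables are meant to describe the participant's cirrhotic liver after SVR. A result taken after a transplant describes a different liver.

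The plan asks for such results at the ET visit and contains no rule that keeps them out of the tables. One participant can therefore be a progression event in one primary display and an apparent improvement in another.

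**Working it through.** There is no sample size or event figure in the plan to reproduce; both documents state that no formal calculation was made. The check follows the record from visit to table and then sizes its effect.

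**1. Does windowing lose the ET record?** No. The windows in SAP Table 3-1 cover every study day from 1 onward without gap or overlap, and those in Table 3-2 cover every day from -75 onward.

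**2. Is the ET record the one selected?** Assume scheduled visits fall on the nominal days 168k (k = 1 to 9). The laboratory window around day 168k closes at 168k + 84 (for example 168 + 84 = 252 for Week 24).
- ET on days 168k + 1 to 168k + 84: same window as the scheduled visit. The scheduled value is nearer the nominal day and is selected.
- ET on days 168k + 85 to 168k + 168: next window, otherwise empty for that participant. The ET value is selected.

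Share selected = 84/168 = 50%. For elastography the spacing is 336 days and the window closes 168 days after the nominal day, so the share is again 168/336 = 50%. The first interval differs. The laboratory baseline window closes at day 30, so ET bloods on days 31 to 168 fall in Week 24, while an ET scan up to day 168 falls in the elastography baseline window.

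The graded-abnormality tables (SAP 6.1.3.2.2.2) use any postbaseline value and the most severe grade, so window selection does not filter them.

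**3. What can one record do?** The SAP formula is MELD = 10 × {0.957 ln(Scr) + 0.378 ln(Tbil) + 1.12 ln(INR) + 0.643}, with values below 1.0 set to 1.0. All laboratory values here are assumptions.

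| Case | Before (Scr, Tbil, INR) | MELD | After | MELD | Change |
|---|---|---|---|---|---|
| A | 1.0, 3.0, 1.8 | 17.17 → 17 | 1.0, 0.8, 1.0 | 6.43 → 6 | -11 |
| B | 1.5, 4.0, 1.9 | 22.7 → 23 | 1.2, 0.8, 1.0 | 8.2 → 8 | -15 |
| C | 1.0, 3.0, 1.8 | 17 | 2.5, 3.0, 1.5 | 23.89 → 24 | +7 |

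Cases A and B move from 15 or above to below 15. Case C stays at 15 or above and shows worsening.

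**4. Effect on a table row.** With t such records among n participants observed in a row, the share in the changed category moves by up to t/n.

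| n | t = 1 | t = 2 | t = 5 |
|---|---|---|---|
| 20 | 5 points | 10 | 25 |
| 100 | 1 | 2 | 5 |
| 1000 | 0.1 | 0.2 | 0.5 |

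One record's contribution to the mean MELD change is change/n. For n = 20 that is -11/20 = -0.55 (A), -15/20 = -0.75 (B) or +7/20 = +0.35 (C). For n = 1000 it is -0.011, -0.015 or +0.007. The documents give neither t nor n.

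**5. Transplant before Day 1.** In inclusion criterion 4 (protocol 4.1, repeated in SAP 1.2) the condition "have not had a liver transplant after receiving a SOF-containing regimen; OR" belongs to the parent-protocol branch. The commercial branch has no such condition, and its Day 1 may come about 2 years after the SVR12 date. A commercial participant transplanted in that interval could contribute donor-liver values from baseline onward. Baseline and follow-up then come from the same liver, so no false shift arises. SAP 6.1.3.2.1 excludes participants with earlier liver events from the event analysis, so no progression event arises either.

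**The case against.** The strongest opposing case is that this is small and traceable. The ET visit is worded as something participants should do, so some will not attend. Participation ends at transplant, so typically one visit per transplanted participant is affected, and the selection rule discards about half of those records from single-value tables. Transplants have their own Kaplan-Meier table and listing, scores and scans are listed by participant and visit, and no hypothesis is tested. All of this stands. It limits the size; it does not supply the missing rule.

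It is also fair that the sentence on all available data covers laboratory summaries only. For CTP, MELD and elastography the point rests on the absence of an exclusion.

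A further objection concerns the remedy. Simply deleting post-transplant values removes participants who progressed to transplant, and the remaining columns then lean towards those doing better. This also stands, and the fix allows for it.

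A reader might infer three stronger things that the documents do not support:
- That donor-liver results count as regression and bias the tables towards it. The SAP has no rule that classifies anyone as regressed, and case C shows that the direction is not fixed.
- That the effect is concentrated in participants decompensated at entry. No transplant counts by CTP class are given.
- That the gap in criterion 4 inflates regression. It does not, for the reasons in step 5.

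**Conclusion.** The gap is real. Followed as written, the plan collects results after an on-study transplant and admits them to the tables that are its only display of regression. The affected value does not describe the native cirrhotic liver, whichever way it moves.

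The size is unknown: per transplanted participant, up to 5 percentage points in a row of 20, 1 point in 100 and 0.1 point in 1000. It would matter in sparse rows and be negligible in large ones. This assumes that the ET visit takes place after the transplant, that earlier visits were near their nominal days, and that the ET record is the one selected. The MELD figures rest on assumed laboratory values.

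This is an inexpensive improvement to the SAP. It does not undermine the Kaplan-Meier analyses of HCC or liver events, which do not use these values. The wording of criterion 4 is a separate, lesser matter: it allows donor-liver values from baseline but creates neither a false shift nor a progression event.

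**What to change.** In SAP 6.1.3.2.2, 6.1.3.2.3 and 6.4.3, add one rule for results dated on or after a liver transplant performed after the SOF-based regimen:
- list and flag them;
- leave them out of by-visit and change-from-baseline summaries, and state whether the graded-abnormality tables follow the same rule;
- show these participants in a separate 'transplanted' category in the shift tables, so that the row total is kept and nobody is silently dropped.

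Flag any commercial participant transplanted between the SOF regimen and Day 1, and leave that participant out of the same summaries. The varices table in SAP 6.4.2 needs no change on account of the ET visit, because endoscopy is not on the ET list.

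The cost is slightly fewer values at the visits concerned and one more table category. No new data should be needed: protocol 6.3.5 records transplants before Day 1 and during the study, and the planned time-to-transplant table already requires a date. If the SAP is not reopened, SAP section 1 provides for later changes to be documented in the CSR.

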### **8.6.2. Secondary Analyses**

The proportion of subjects with detectable HCV RNA due to re-emergence of pre-existing virus through Week 240 will be summarized by number and percent of subjects by time point using the same model as in the primary analysis.

The proportion of subjects with detectable HCV resistance mutations through Week 240 will be summarized by number and percent of subjects by time point.

The proportion of subjects with detectable HCV RNA due to re-infection through Week 240 will be summarized by number and percent of subjects by time point.

Clinical laboratory test results related to liver disease progression or regression (ie, ALT, AST, bilirubin, albumin, platelets, PT and/or INR, and  $\alpha$ -fetoprotein) will be listed by subject. Reference ranges provided by the laboratory for each parameter will be used to evaluate the clinical significance of laboratory test results. Values falling outside of the relevant reference range will be flagged, as appropriate, in the data listings. Abnormalities in clinical laboratory test results will be summarized by enumeration of the number of subjects with values falling outside of the reference range by study day. Laboratory data will be descriptively summarized over time by study day and by the change from Baseline.

Clinical signs and symptoms related to liver disease progression or regression will be summarized by frequency and percent of subjects. Applicable clinical signs assessed include ascites, hepatic encephalopathy, varices, spontaneous bacterial peritonitis, HCC and transplant. In addition, Child-Turcotte-Pugh score will be included with the following categories, A (5-6), B (7-9), and C (10-15).

Descriptive summaries and listings will be provided for additional efficacy evaluations of the quality of life endpoints.

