6.5. Changes from Protocol-Specified Endpoint Analyses

No change from protocol-specified endpoint analysis is planned.

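### The SAP drops the protocol's by-visit count of out-of-range liver tests without declaring it, and its worst-grade table shows only worsening and counts any graded value as new when baseline is missing

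*SAP*

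**What the plan says.** Protocol 8.6.2 (Secondary Analyses) names the tests it regards as related to progression or regression of liver disease: ALT, AST, bilirubin, albumin, platelets, PT and/or INR, and alpha-fetoprotein. Abnormal results are to be "summarized by enumeration of the number of subjects with values falling outside of the reference range by study day". The same section adds: "Laboratory data will be descriptively summarized over time by study day and by the change from Baseline".

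SAP 6.1.3.2.2 uses the reference range only to flag values in the hematology, coagulation and chemistry listings. Alpha-fetoprotein goes to a separate listing, for which no flag is mentioned. The tabulated abnormalities come from SAP 6.1.3.2.2.2, which has four relevant rules:

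- Definition: "Laboratory abnormalities are defined as values that increase at least 1 toxicity grade from baseline for any postbaseline value".
- Missing baseline: "If the relevant baseline laboratory value is missing, then any abnormality of at least Grade 1 will be considered a laboratory abnormality".
- Unit of summary: "Participants will be categorized according to the most severe postbaseline abnormality grade for a given analyte".
- Denominator: "The denominator for graded laboratory abnormality summaries is the number of participants with non-missing postbaseline values".

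SAP 6.5 then states: "No change from protocol-specified endpoint analysis is planned".

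**The concern.** The second primary endpoint (Protocol 8.1.2, SAP 6.1.1) is a proportion with progression or regression, judged on laboratory as well as clinical parameters. A count at each visit can move in either direction. A worst-ever grade cannot: one transient rise fixes a participant's row for the whole study, and a fall in grade has no row. The percentage also depends on how many visits a participant attended. That may differ between the regimen groups being displayed, because the sponsor may withdraw subjects from individual treatment protocols (Protocol 3.1), and transplant or virologic failure ends participation (Protocol 3.2).

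The missing-baseline rule in effect sets an unknown baseline to Grade 0. In a cohort selected for cirrhosis, where abnormal liver tests often pre-date entry, that is a poor default. A reader of the clinical study report would have no sign that a protocol table had been replaced.

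**Working it through.** The documents give no figure on this point, so the check is mainly a comparison of text.

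**1. Protocol table against SAP table**

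| Feature | Protocol 8.6.2 | SAP 6.1.3.2.2.2 |
|---|---|---|
| Yardstick | Laboratory reference range | Toxicity grade, relative to baseline |
| Time | Each study day | Any postbaseline value, worst grade kept |
| Direction | Count can rise or fall | Worsening only |
| Unchanged abnormality, baseline known | Counted at every visit | Not counted |
| Unchanged abnormality, baseline missing | Counted at every visit | Counted as an abnormality |

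The two tables answer different questions, so one does not stand in for the other.

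**2. What the display can show.** Take three participants on one analyte, with baseline known.

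- Grade 1 at baseline, Grade 2 at Week 24, Grade 0 from Week 48 onward: tabulated at Grade 2.
- Grade 2 at baseline, Grade 0 at every later visit: no abnormality.
- Grade 2 at baseline and at every later visit: the rise is 2 − 2 = 0, so no abnormality.

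The second and third are indistinguishable, although one recovered and the other did not.

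**3. Accumulation over visits.** There are 10 scheduled postbaseline visits (Weeks 24 to 240). Having a rise at any visit so far can only become more frequent as visits are added. To illustrate the size, a stable cohort of 200,000 was simulated. Each participant had one baseline and 10 later values, with constant within-person correlation r and no true change. Grades 1 to 4 began at the 70th, 85th, 95th and 99th percentiles. The correlations and cut-offs are assumptions; the documents give neither.

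| r | Grade up at one visit | Grade down at one visit | Grade up at any of 10 |
|---|---|---|---|
| 0.95 | 8.8% | 8.7% | 26.6% |
| 0.90 | 11.5% | 11.5% | 35.1% |
| 0.80 | 14.5% | 14.5% | 45.5% |
| 0.70 | 16.6% | 16.4% | 53% |
| 1.00 | 0% | 0% | 0% |

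At a single visit, rises and falls balance, as they must in a stable cohort. The SAP table reports only the last column. An out-of-range count in the same cohort would sit at about 30% at every visit. That follows from placing the Grade 1 cut-off at the 70th percentile. It is a prevalence and should not be set against a rate of grade rise.

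**4. Missing baseline.** A participant stably at Grade 1 is not counted if baseline is known (1 − 1 = 0) and is counted if it is missing. Let m be the share with a missing baseline and q the share of those stably at Grade 1 or higher. The share of the cohort wrongly counted as new is m × q. Both inputs are assumed:

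- Low: 0.01 × 0.20 = 0.2%.
- Middle: 0.05 × 0.20 = 1% to 0.05 × 0.50 = 2.5%.
- High: 0.10 × 0.50 = 5%.

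The laboratory baseline window in SAP Table 3-1 is Days 1 to 30. A first draw on Day 31 is assigned to Week 24 and leaves baseline missing.

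**The case against.** The strongest reply is that by-visit change and recovery are shown elsewhere. SAP 6.1.3.2.2.1 summarizes values and change from baseline for each test at each visit, which meets the second protocol sentence quoted above. There are shift tables for FibroTest, ELF and FIB-4, the last with a category for a 25% reduction. CTP class and MELD are summarized by visit with shifts. SAP 6.1.3.2.2.2 also promises by-visit counts for categorical laboratory data. A cumulative count exceeding a single-visit count is what a cumulative summary does and is not an error. There is no hypothesis testing, and SAP 5.1 tabulates duration of follow-up by group.

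Much of this stands and limits the consequence, but it does not fill the gap. Means and changes give no proportions. CTP and MELD contain no platelets, ALT, AST or alpha-fetoprotein. FIB-4 merges age, AST, ALT and platelets. The sentence on categorical data does not say that continuous tests will be classified against the reference range.

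A reader might infer three stronger points, none of which the documents support.

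- *Stable cirrhosis in general is counted as laboratory worsening.* With a known baseline a rise of at least one grade is required. The direct miscount is confined to missing baselines. For everyone else the issue is that transient rises accumulate.
- *The worst-grade table overstates the by-visit table by a calculable factor.* An assumed chance of a grade rise per visit is not the protocol's quantity, which is the share out of range. The grading scale's cut-offs are also not reproduced in the SAP.
- *Transfers from GS-US-248-0122 lack a baseline by design.* Protocol 6.1.1 spares a duplicate draw when both visits fall on one day. Neither document says that the shared result is not carried over.

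**Conclusion.** The point holds as a reporting gap with two parts. First, a protocol-specified per-analyte table is absent from the SAP. Its nearest substitute shows one direction only and accumulates over up to 10 visits, and SAP 6.5 reports no change. This rests on the text alone. Second, the missing-baseline rule, combined with a denominator that needs only a postbaseline value, counts pre-existing abnormality as new. The direction is certain, but the size is not given. The 0.2% to 5% range depends wholly on assumed rates, and the 30-day baseline window probably keeps the number small.

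The effect is bounded. SAP 6.1.3.2.1 builds the Kaplan-Meier progression analysis from clinical events, transplant and liver-related death, so these tables cannot alter it. The SAP calls the rows laboratory abnormalities, not progression, although they sit under the progression/regression endpoint. What is at risk is how the laboratory part of that endpoint is read.

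**What to change.** - Add the protocol's table: number and percent outside the reference range at baseline and at each visit, for each test named in Protocol 8.6.2. A baseline-to-visit grade shift (improved, same, worse) per analyte can be added or, if declared, used instead.
- In the worst-grade table, show participants with a missing baseline on a separate row instead of counting them as new abnormalities, and report how many there are.
- Record any remaining departure from Protocol 8.6.2 in SAP 6.5. As the SAP is already final, the clinical study report is the alternative, which SAP Section 1 provides for.

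The cost is SAP or report wording and a few standard tables from visit-level data that are already collected.
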